APPENDIX 2: ECG – NORMAL RANGES55

ABBREVIATIONS

Abbreviation	Definition or Description
ADHD	Attention deficit hyperactivity disorder
AE	Adverse Event
ALT	Alanine-Aminotransferase
AST	Aspartate-Aminotransferase
ATC	Anatomical Therapeutic Chemical
BA	Bone Age
BMI	Body Mass Index
CA	Chronological Age
cm	Centimeter
C _{max}	Maximum Value of Concentration
CRF	Case Report Form
CSR	Clinical Study Report
DBP	Diastolic Blood Pressure
ECG	Electrocardiogram
EMA	European Medicines Agency
FDA	Food and Drug Administration
ft3	Free Triiodothyronine
ft4	Free Thyroxin
GGT	Gamma-Glutamyl Transferase
GH	Growth Hormone
GHD	Growth Hormone Deficiency
HbA1c	Hemoglobin A1c
HDL	High-Density Lipoprotein
hGH	Human Growth Hormone
HR	Heart Rate
HT	Height
HV	Height Velocity
ICF	Informed Consent Form
ICH	International Conference on Harmonisation
IGF-1	Insulin-Like Growth Factor 1
IGFBP-3	Insulin-Like Growth Factor Binding Protein 3
ITT	Intent-to-treat
ISC	Independent Safety Monitoring Committee
ISRs	Injection Site Reactions
kg	Kilogram
LDH	Lactate Dehydrogenase
LDL	Low-Density Lipoprotein
m ²	Square Meter
mL	Milliliter
µg	Microgram
MAR	Missing at Random
MCMC	Markov Chain Monte Carlo

MedDRA	Medical Dictionary for Regulatory Activities
MM	Medical Monitor/Expert
MMRM	Mixed Model for Repeated Measures
MRI	Magnetic Resonance Imaging
ng	Nanogram
PD	Pharmacodynamic
PEG	Polyethylene Glycol
PK	Pharmacokinetic
PP	Per Protocol
RR	Respiratory Rate
SAE	Serious Adverse Event
SAP	Statistical Analysis Plan
SBP	Systolic Blood Pressure
SD	Standard Deviation
SDS	Standard Deviation Score
SE	Standard Error
SOC	System Organ Class
TEAE	Treatment-emergent Adverse Event
TSH	Thyroid-Stimulating Hormone
WHO	World Health Organization

1. Overview

This Statistical Analysis Plan (SAP) describes and supplements the planned analysis and reporting for Ascendis Pharma Endocrinology Division A/S protocol TransCon hGH CT-301 (A multicenter, Phase 3, randomized, open-label, active-controlled, parallel-group trial investigating the safety, tolerability, and efficacy of TransCon hGH administered once a week versus standard daily hGH replacement therapy over 52 weeks in prepubertal children with growth hormone deficiency (GHD)), Final Version 1.0 dated 4 August 2016, and Amendment 1 dated 12 Sept 2017.

The structure and content of this SAP provides sufficient detail to meet the requirements identified by the Food and Drug Administration (FDA), European Medicines Agency (EMA), and International Conference on Harmonization (ICH) of Technical Requirements for Registration of Pharmaceuticals for Human Use: Guidance on Statistical Principles in Clinical Trials [1]. All work planned and reported for this SAP will follow internationally accepted guidelines, published by the American Statistical Association [2] and the Royal Statistical Society [3], for statistical practice.

The planned analysis identified in this SAP may be included in clinical study reports (CSRs), regulatory submissions, or future manuscripts. Also, post-hoc exploratory analyses not necessarily identified in this SAP may be performed to further examine study data. Any post-hoc, or unplanned, exploratory analyses performed will be clearly identified as such in the final CSR.

The following documents were reviewed in preparation of this SAP:

Clinical Research Protocol TransCon hGH CT-301, and Case Report Forms (CRFs) for Protocol TransCon hGH CT-301.

ICH Guidance on Statistical Principles for Clinical Trials (E9).

The reader of this SAP is encouraged to also read the clinical protocol, and other identified documents, for details on the planned conduct of this study. Operational aspects related to collection and timing of planned clinical assessments are not repeated in this SAP unless relevant to the planned analysis.

2. Study Objectives and Endpoints

2.1 Study Objectives

2.1.1 Primary Objective

The primary objective is to evaluate and compare the annualized height velocity of prepubertal children with growth failure due to GHD treated with weekly TransCon hGH to that of a commercially available daily hGH formulation at 52 weeks.

2.1.2 Secondary Objectives

The secondary objectives are:

- To evaluate the safety of weekly TransCon hGH administered over 52 weeks compared to daily hGH
- To evaluate and compare the annualized height velocity over 52 weeks of weekly TransCon hGH to daily hGH
- To evaluate and compare the change in height standard deviation score (SDS) over 52 weeks of weekly TransCon hGH to daily hGH
- To evaluate the change in serum insulin-like growth factor 1 (IGF-1) and insulin-like growth factor binding protein 3 (IGFBP-3) and the change in IGF-1 SDS and IGFBP-3 SDS; and the normalization of IGF-1 SDS over 52 weeks of weekly TransCon hGH or daily hGH
- To describe the PK/PD profile of TransCon hGH, hGH, IGF-1, IGF-1 SDS, IGFBP-3, IGFBP-3 SDS and Polyethylene Glycol (PEG) administered as a weekly injection (PK/PD subset; TransCon hGH cohort only)
- To compare the C_{max} for hGH of TransCon hGH to the anticipated C_{max} of daily hGH
- To determine the incidence of anti-hGH antibodies for both treatments, and treatment emergent anti-PEG antibodies for TransCon hGH over 52 weeks

2.2 Efficacy, Safety, and PK/PD Endpoints (Target Variables)

2.2.1 Efficacy Variables

The primary efficacy variable (endpoint) is:

Annualized HV at 52 weeks for weekly TransCon hGH and daily hGH treatment groups

The secondary efficacy variables (endpoints) are:

- Annualized HV for the TransCon hGH and the daily hGH treatment group over 52 weeks
- Change in height (HT) SDS over 52 weeks for the TransCon hGH and the daily hGH treatment group
- Serum IGF-1 and IGFBP-3 levels and IGF-1 SDS and IGFBP-3 SDS; and the normalization of IGF-1 SDS over 52 weeks for the TransCon hGH and the daily hGH treatment group

2.2.2 Safety Variables

The primary safety variables (endpoints) are:

- Incidence of AEs
- Local tolerability (assessed by the subject, the parents/legal guardians and the investigator)
- Incidence of anti-hGH antibodies including neutralizing antibodies as needed (both cohorts) and incidence of treatment-emergent anti-PEG antibody formation (in TransCon hGH subjects)

- IGF-1 levels and IGF-1 SDS
- Parameters of glucose metabolism (fasting glucose and insulin level, Hemoglobin A1c (HbA1c)) and lipid parameters
- Hormone levels: thyroid status and morning cortisol
- All other hematology and biochemistry blood parameters
- Electrocardiograms (ECG)
- Results of the physical examinations, vital sign measurements
- Bone age (BA) at 52 weeks

2.2.3 Pharmacokinetic/Pharmacodynamic Variable(s)

The pharmacokinetic (PK) variables (endpoints) are:

Subset of at least 8 TransCon hGH treated subjects after 13 weeks of treatment:

- PK profile of TransCon hGH over 1 week
- PK profile of hGH over 1 week
- PK profile of PEG over 1 week
- C_{max} for hGH of TransCon hGH

The pharmacodynamic (PD) variables (endpoints) are:

- PD profile of IGF-1 and IGFBP-3 over 1 week
- PD profile of IGF-1 SDS and IGFBP-3 SDS over 1 week

3. Overall Study Design and Plan

This is a phase 3, randomized, open-label, active-controlled trial of TransCon hGH as compared to standard daily growth hormone, over 52 weeks (Figure 1). The trial will be conducted at approximately 100 sites in approximately 20 countries in North America, Europe, Middle East and North Africa, and Oceania. All centers will be specialized treatment centers in the management of pediatric GHD.

The trial consists of:

[figure not shown]
- Screening period - up to 6 weeks (plus approximately 2 weeks between randomization and V1)
- Treatment period - 52 weeks of dosing

The total duration of participation for each subject in the trial will therefore be up to about 60 weeks.

PK/PD profiling and electrocardiogram (ECG) screening bracketing presumed C_{max} of TransCon hGH, hGH, IGF-1, and PEG will be established in a subset of at least 8 TransCon hGH treated subjects (PK/PD subset).

All subjects who successfully complete the 52-week randomized trial will be invited to participate in an extension trial after the treatment period of this 52-week trial has ended. This extension period is to assess long-term safety and efficacy. Subjects on Genotropin treatment (Cohort 2) will be switched over to TransCon hGH treatment for this extension trial.

Figure 1

3.1 Measures Taken to Minimize Bias

Once all results determining the eligibility of the subject are available and reviewed by the Medical Monitor/Expert (MM), the subject will be centrally allocated to 1 of 2 cohorts: either TransCon hGH or Genotropin, in a 2:1 ratio, and allocated to strata using the minimization rule according to their age (≤ 6 and > 6 years), peak growth hormone (GH) levels in stimulation tests (≤ 5 ng/mL and > 5 ng/mL), and gender. For the stratum peak GH levels in stimulation tests (≤ 5 ng/mL and > 5 ng/mL), the stratum will be allocated based on the highest GH value of the 2 stimulation tests. The subject will be assigned a unique randomization number along with the cohort allocation. The trial auxologists will be trained and kept blinded to treatment allocation as far as possible at each site.

All efforts will be made to keep missing data to a minimum, including the following:

1. Investigators will be trained about the importance of retention
2. Investigators will be instructed to encourage complete follow-up for all subjects, including any subjects who might discontinue either weekly TransCon hGH or daily Genotropin therapy
3. The Informed Consent Form (ICF) and Assent Form will include a statement educating subjects and parents/legal guardians about the scientific importance of their data even if the subject discontinues study treatment early
4. Special efforts will be made to provide assistance to subjects/families who might discontinue due to travel or cost barriers, such as offers of transportation to the clinic
5. Most visits have visit windows to allow flexibility of clinic attendance (see Sections 10.1.2.1 and 10.1.2.2 of protocol)
6. Every effort will be made to contact subjects/legal guardians or other family members in order to maintain contact with the clinic

This is an open-label trial. Due to different dose frequencies and dosing techniques, it is not deemed suitable to employ blinding methods between TransCon hGH and Genotropin treatment assignment. However, attempts will be made to keep the the Sponsor staff (especially the MM) blinded to treatment. Any necessary unblinding to the Sponsor staff for safety purposes will be documented before database lock.

Subjects will be identified by a Subject Number (allocated at Screening), consisting of 3 digits to indicate the site and 2 digits specific for the subject.

3.2 Sample Size and Subject Population

This is a pivotal clinical trial intended to support market approval.

Based on the Phase 2 trial (Protocol ACP-001_CT-004) and similar growth hormone studies published in the literature, and assuming a SD of 3.5 cm/year with a non-inferiority margin of 2.0 cm, a sample size of 147 subjects in the ITT population will be needed to show non-inferiority of TransCon hGH treatment compared to daily hGH with a power of 90%. This sample size calculation is based on a 2:1 randomization and a 1-sided alpha level of 0.025.

A sample size of 150 subjects randomized has been chosen to account for slight imbalances in the randomization due to stratification of randomization. For 150 enrolled subjects, approximately 450 subjects may need to be screened in the trial.

Approximately 150 prepubertal, hGH-treatment naïve children (males and females) with GHD will be included. Subjects will be allocated to 1 of 2 treatment groups in a 2:1 ratio:

- Two thirds of the 150 subjects (approximately 100 subjects) will receive TransCon hGH treatment to obtain an expected 90 per protocol subjects in this cohort
- One third of the 150 subjects (approximately 50 subjects) will receive Genotropin treatment to obtain an expected 45 per protocol subjects in this cohort

4. Analysis and Reporting

4.1 Interim Analysis

No interim analysis is planned. An independent safety monitoring committee (ISC) will be established to monitor subject safety. Data used for ISC meetings will be handled according to the ICH E9 guidelines and therefore will not affect the study design and conduct from the efficacy perspective.

4.2 Final Analysis

All final, planned analyses identified in the protocol and in this SAP will be performed after the last subject has completed the last study visit and end of study assessments, and all relevant study data have been processed and integrated into the analysis data base. Any results from unplanned analyses (post-hoc) will be clearly identified in the text of the CSR.

5. Analysis Populations

The following analysis populations are planned:

Safety Analysis Population: The safety analysis population will include all randomized subjects who have received at least 1 dose of active treatment.

Intention-To-Treat Population (ITT): The Intent-to-Treat population will include all randomized subjects who have received at least one dose of active treatment

Pharmacokinetic/Pharmacodynamic Population (PK/PD): The PK/PD Population includes all subjects in the Safety Population who have PK/PD assessments. The PK/PD profile subset comprise a subset of subjects pre-identified as the PK/PD subset from the TransCon hGH cohort who attended Visit 3 as planned, and from whom blood samples were taken at time points predose, 8, 12, 16, 24, 36, 48, 72, 96, 120, and 168 hours postdose. All subjects in the safety analysis population with additional PK/PD samples will be included in additional PK/PD analyses.

Per Protocol Population (PP): The basis of PP population is the ITT population who have relevant data evaluable for the primary efficacy endpoint of annualized HV at 52 weeks. Specifically, subjects were excluded from the PP population if they:

- Had a diagnosis known to impact growth (exclusion criteria 4, 5, 6, 10, 12, 13)
- Took the wrong treatment (eg. randomized to TransCon hGH cohort but took Genotropin in error)
- Missed or overdosed on at least 5 doses of TransCon hGH, or 35 doses of Genotropin
- Used prohibited concomitant medications at trial entry (exclusion criteria 15, 16)
- Failed to have a height measurement at the Week 52 visit

Given that the primary objective of the study is based on testing for non-inferiority, the primary efficacy analyses will be performed on both ITT and PP populations. The primary analysis population is the ITT population. The ITT population will be analyzed on the basis of the intention to treat a subject, i.e. the planned treatment regimen. The PP subset will be analyzed on the basis on the actual treatment given.

The safety analyses will be based on the Safety Analysis Population.

6. General Issues for Statistical Analysis

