9.9.2 Permitted and Prohibited Therapies

Concomitant therapy is considered any medication other than the investigational or reference product that is administered from the first day of study drug administration up until the end of the trial. Any change in documented, permitted concomitant medication being taken at the beginning of the clinical trial must be recorded in the eCRF, noting the type of medication, the dose, duration, and indication. If the administration of a prohibited concomitant medication becomes necessary, participation in the trial may be discontinued prematurely for that subject, based on a decision made in collaboration with the Medical Expert and Sponsor.

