13.3. Analysis Populations

The following data subsets will be analyzed:

Safety Analysis Subset – The safety analysis set will include all randomized subjects who have received at least 1 dose of active treatment.

Intent-to-treat Subset – The ITT subset will include all randomized subjects who have received at least 1 dose of active treatment and have follow-up efficacy data.

Per-protocol Subset – The basis of PP subset is the ITT set. Subjects with major protocol deviations will be excluded from the PP analysis. Major protocol deviations excluding subjects from the Per-protocol analysis set will be defined in the SAP.

PK/PD Population – The PK/PD population includes a subset of subjects from the TransCon hGH cohort who attended Visit 3 as planned and from whom blood sampling was performed at time points predose, 8, 12, 16, 24, 36, 48, 72, 96, 120, and 168 hours postdose.

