7.2 Protocol Violations and Deviations

A list of major protocol deviations that could significantly affect study assessments will be identified. The incidence of major protocol deviations will be presented by treatment group for all randomized subjects if appropriate.

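### The per-protocol set ignores prohibited drugs started on study and entry breaches of exclusion criteria 2, 7 and 14

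*SAP*

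**What the plan says.** SAP section 5 starts from ITT children with evaluable Week 52 data and then names five grounds for leaving PP, with no wording that leaves the list open:

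- a growth-affecting diagnosis: "Had a diagnosis known to impact growth (exclusion criteria 4, 5, 6, 10, 12, 13"
- the wrong treatment taken
- a dosing threshold: "Missed or overdosed on at least 5 doses of TransCon hGH, or 35 doses of Genotropin"
- prohibited drugs: "Used prohibited concomitant medications at trial entry (exclusion criteria 15, 16"
- no Week 52 height.

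No other text sets PP membership. Protocol 13.3 hands the matter over: "Major protocol deviations excluding subjects from the Per-protocol analysis set will be defined in the SAP". SAP 7.2 says "A list of major protocol deviations that could significantly affect study assessments will be identified" and promises incidence by arm, but does not connect that list to PP.

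On drugs, protocol 9.9.2 treats as concomitant any non-study medication "administered from the first day of study drug administration up until the end of the trial". Protocol 9.9.2.2 and SAP 9.10 prohibit estrogen, anabolic steroids, systemic corticosteroids beyond the stated doses, and weight-reducing or appetite-suppressing drugs other than for ADHD. On the consequence, protocol 9.9.2 says "If the administration of a prohibited concomitant medication becomes necessary, participation in the trial may be discontinued prematurely for that subject". Protocol 7.3.1 likewise lists such use as a reason for which participation may end.

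SAP 3.2 describes the children to be enrolled as prepubertal, not previously treated with hGH, and having GHD. SAP section 5 runs the primary analysis in both ITT and PP because the objective is non-inferiority, and names ITT as the primary population.

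**The concern.** In a non-inferiority trial the PP analysis is there to show whether departures from the protocol have hidden or created a difference between arms. A PP set that keeps children who took a growth-affecting prohibited drug for part of the year, or who were never in the target population, does that job less well on exactly those points.

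The limit to trial entry is not explained by a wish to avoid exclusions based on events after randomisation. The wrong-treatment, dosing and Week 52 height items are all of that kind.

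At stake is how well PP checks the ITT result. The direction of any distortion is not fixed. Slower growers kept in the Genotropin arm, or faster growers kept in the TransCon arm, push the difference (TransCon minus daily) up. The reverse cases push it down.

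**Working it through.** **Text check.** The PP items name exclusion criteria 4, 5, 6, 10, 12, 13, 15 and 16. Set against the three attributes in SAP 3.2 and the numbering in protocol 8.1.2:

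| Attribute of target population | Exclusion criterion | Named in the PP list? |
|---|---|---|
| Prepubertal | 14 (Tanner stage above 1) | No |
| hGH-naive | 2 (prior hGH or IGF-1) | No; current growth-affecting treatment at entry falls under 15, past exposure does not |
| GHD | 7 (idiopathic short stature) | No |

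**Path of a child through the list.** Suppose a child starts a prohibited drug mid-trial, continues study treatment and attends Week 52. The diagnosis item does not apply, the treatment was the right one, the doses were taken, nothing prohibited was used at entry, and the height exists. The child is in PP.

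**The plan's own sample size.** Inputs from SAP 3.2: SD 3.5, margin 2.0, one-sided alpha 0.025, power 90%, 2:1 allocation. A true difference of 0 is assumed because none is stated.

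Control n = (1.960 + 1.282)² × 3.5² × (1 + 1/2) / 2.0² = 48.3, rounded up to 49. The total is 3 × 49 = 147, which reproduces the stated figure.

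**Precision of PP at its expected size.** SAP 3.2 expects 90 and 45 per-protocol children.

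- SE = 3.5 × √(1/90 + 1/45) = 0.639
- 95% half-width = 1.96 × 0.639 = 1.25 cm/year
- Power at no true difference = Φ(2.0/0.639 − 1.96) = 87.9%

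**Illustrative shift.** Assumption, not from the documents: k affected children in one arm, each differing by 3 cm/year from the rest of that arm. The shift is k × 3/45 in Genotropin or k × 3/90 in TransCon.

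| k | All in Genotropin | All in TransCon |
|---|---|---|
| 1 | 0.07 | 0.03 |
| 3 | 0.20 | 0.10 |
| 6 | 0.40 | 0.20 |

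For k = 3 this is 0.20/0.639 = 31% or 0.10/0.639 = 16% of one SE, and 10% or 5% of the margin. The shift is proportional to the assumed deviation, so half the deviation gives half the shift.

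**Precision lost by three more exclusions.**

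| PP size (TransCon/Genotropin) | SE | Half-width | Power |
|---|---|---|---|
| 90/45 | 0.639 | 1.25 | 87.9% |
| 87/45 | 0.643 | 1.26 | 87.5% |
| 90/42 | 0.654 | 1.28 | 86.4% |

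**The case against.** The strongest reply is that nothing is decided on PP. SAP 8.6 tests non-inferiority on the primary analysis, and ITT is the primary population. That stands. A reader might infer that the trial's conclusion is at risk, and the documents do not support that.

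Second, the gaps may be nearly empty. The Medical Expert verifies eligibility before randomisation, and a child withdrawn for prohibited drug use will usually lack a Week 52 height and leave PP anyway. This limits the likely numbers but does not close the gap. Withdrawal is optional, and the Version 5.0 entry in the SAP document history records only two early discontinuations, so that route can remove very few children. Affected children would also appear in the planned deviation and prohibited-medication listings, but a listing does not change the PP estimate.

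Third, extending the drug item adds exclusions based on events after randomisation in an open-label trial, where drug use may itself depend on the arm. The corticosteroid limit in protocol 9.9.2.1 (approximately one month in a calendar year, in inhaled-budesonide equivalents) is also not a sharp threshold. Both points stand, and they are why membership needs blinded review with recorded reasons.

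Three wider readings are tempting and do not hold:

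- *Criterion 8 (coeliac disease, hypothyroidism, rickets) is also missing.* Criterion 10 is listed, and its open wording reaches active disease likely to affect growth. Stably replaced thyroid deficiency is eligible under inclusion criterion 8.
- *The list omits part of a documented set of growth-related criteria.* No document defines such a set. The case for criteria 2, 7 and 14 rests on the SAP's own description of the target population.
- *The dosing item is unusable because a missed dose is undefined.* SAP 6.2 defines planned doses and SAP 9.11 counts actual doses, so a working count is available.

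Puberty that begins during the trial is not a breach of criterion 14 and is not part of this point.

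**Conclusion.** The point holds for the supportive analysis. As written, PP keeps a child who uses a prohibited drug on study and reaches Week 52. It also keeps a child who entered with past hGH or IGF-1 exposure, idiopathic short stature or Tanner stage above 1. This follows from the text and needs no assumption.

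The size is unknown. The shifts shown rest on assumed counts and an assumed 3 cm/year deviation, together with the SAP's SD and expected PP sizes. A few affected children would move the PP difference by a fraction of its standard error, in either direction; if there are none, the edit changes nothing. It is a cheap improvement that should be made, and it does not challenge the primary result.

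**What to change.** In SAP section 5:

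1. Extend the drug item to cover use at trial entry (exclusion criteria 15 and 16) or, during the treatment period, any therapy prohibited by protocol 9.9.2.2. This applies the protocol's existing prohibitions to PP membership and sets no new clinical rule.
2. Add an item for entry violations of exclusion criteria 2, 7 and 14.
3. Have reviewers blinded to treatment decide membership and record the reason before unblinding. The Version 3.0 entry in the SAP document history already describes blinded finalisation of the PP criteria.

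If unblinding has already happened, keep the existing PP set as the prespecified one and report the revised set as a labelled post-hoc sensitivity analysis. SAP 4.2 provides for this: "Any results from unplanned analyses (post-hoc) will be clearly identified in the text of the CSR".

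The cost is SAP wording and some programming. The data are already planned as listings (exclusion criteria and protocol deviations under 16.2.2, prohibited medications under 16.2.9). The downside is a few more post-randomisation exclusions from PP and, for three of them, the small loss of precision tabulated above.
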